14.3 Reporting of Adverse Events

All AEs must be monitored and followed until they are adequately resolved or explained. The PI or the Study Coordinator at each Clinical Site is responsible for entering any and all reportable AEs into the database within the required timelines and updating the information (e.g., date of resolution, action taken) in a timely manner. All reportable events must be submitted to WebDCU via the AE CRF within 5 days of first knowledge of the event. Upon completion of the study protocol by the subject, premature withdrawal from the study by the subject, or the subject's death, all information regarding each reportable event must be completed, if not done so earlier. In the event of a subject death during study, that should be immediately reported and all possible efforts should be made by the site to obtain relevant records from the hospital or the subject's primary care provider to determine the cause of death.

14.4 Medical Safety Monitor

An Independent Medical Safety Monitor has been appointed to review all serious adverse events (SAEs) reported during the study. The MSM will adjudicate the relationship of the SAE to both the study intervention and the principles and intensity of overall care as described in the protocol as well as enter the expectedness of the reported SAE. In addition, the MSM will regularly review aggregated AE data (provided by the SDCC). The MSM will present any concerns regarding safety to the Study Executive Committee and the DSMB Liaison.

14.5 DSMB

The SHARP study will have an independent Data and Safety Monitoring Board (DSMB) appointed by the NIDDK to oversee study patient safety. The DSMB will receive reports on study progress and safety as well as data quality. The DSMB will meet in person or by teleconference on a minimum of a semi-annual basis to monitor cumulative safety data and data quality.

15. STATISTICAL CONSIDERATIONS

15.1 Sample Size and Power Estimation

Since the natural history of iRAP is poorly understood, risk estimates are based on previous small clinical trials and epidemiological studies. Based on a previous small trial of ERCP for RAP in pancreas divisum with limited (1-year) follow-up for the majority of patients, the probability of developing a third episode of AP is 70%.(Lans, Geenen et al. 1992) Natural history studies specific to divisum are lacking, but retrospective cohort studies and one surgical series suggest the recurrence rate following minor papilla stenting, miES, or surgical sphincteroplasty are 15-50%(Attwell, Borak et al. 2006, Chacko, Chen et al. 2008, Borak, Romagnuolo et al. 2009, Crino, Bernardoni et al. 2017). Given the short-term risk of post-ERCP pancreatitis (~10%), costs of ERCP, and potential for post-sphincterotomy re-stenosis, we believe a minimum effect size of 33% (relative risk reduction) is of clinical relevance. This effect size was agreed upon by the site principal investigators as the least clinically significant benefit for ERCP, considering the risks of ERCP and available data on this topic. Since AP recurrence is variable and time sensitive, we propose a reduction in risk of subsequent acute pancreatitis during follow-up as the primary outcome, defined by the median time to acute pancreatitis recurrence (a time-to-event measure). We assume the risk of recurrence within 12 months of randomization is 60% in EUS + sham and 40% in EUS + ERCP with miES groups, with the median time to recurrence being 9.1 and 16.3 months for EUS + sham and EUS + ERCP with miES groups, respectively. Assuming an exponential hazard, a 2-sided alpha error of 5%, power 85%, and non-adherence of 20% (this includes technical crossovers when sphincterotomy cannot be performed and competing events/risks), the trial requires a total sample size of approximately 234 (n=117 per group).

We recognize that sample size estimation is based on assumptions and if the event rate is lower than assumed, we may begin to see a decrease in power. To reduce the likelihood of an underpowered study due to incorrect assumptions, a sample size re-estimation will be conducted during the enrollment period. Details of this plan as well as all statistical considerations are outlined in the SHARP Statistical Analysis Plan.

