4. OBJECTIVES

4.1 Primary outcome (Aim #1): Reduce the risk of subsequent acute pancreatitis episodes by 33%.

To test this aim, we will compare the incidence of acute pancreatitis > 30 days after treatment allocation as the primary outcome measure, using the next attack of acute pancreatitis as a time-to-event outcome.

4.2 Secondary outcome (Aim #2): To compare the incidence rate ratio of acute pancreatitis between treatment groups.

All randomized patients will be followed longitudinally until study completion, even if acute pancreatitis occurs during follow-up. A secondary benefit of miES may be a reduction in acute pancreatitis frequency, defined as the incidence rate (episodes/time pre- and post-randomization). Since baseline incidence rate is a probable predictor of post-randomization incidence rate, we will compare the incidence rate ratios between the two arms, keeping person-time equal between the pre/post periods.

4.3 Secondary outcome (Exploratory Aim #3): To compare changes in patient-centered outcomes between treatment groups.

The natural history of idiopathic RAP is primarily based on retrospective cohort studies with variable follow-up. We will measure relevant patient-centered outcomes, using validated instruments for each: pain, self-perceived quality of life, global impression of change, pain-related disability, and number and days of pain or pancreas-related hospitalizations.

4.4 Secondary outcome (Exploratory Aim #4): Progression to chronic pancreatitis and its sequelae.

Although the proportion of patients who may transition to chronic pancreatitis during the proposed time period of the study will be low, we will quantify the progression to chronic pancreatitis during clinical care as an exploratory analysis. To accomplish this, we will perform a secretin-enhanced magnetic resonance imaging (MRI) study with magnetic resonance cholangiopancreatogram (MRCP) at 18 months after enrollment (for those eligible based on enrollment month). Also, we will measure the rates of new-onset diabetes mellitus (using blood glucose and hemoglobin A1c) and exocrine insufficiency (using fecal elastase) at the same time.

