5.4 Estimated Study Duration

In order to maximize follow-up data, we will follow all patients every 6 months until the end of Year 4.5 of the U01 funding period, when the database will be locked for analysis. We estimate starting enrollment within 6 months of the grant start date and completing enrollment over 3.5 years. Assuming consistent enrollment, this would provide us with a minimum follow-up of 6 months and maximum follow-up of 48 months.

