15.3 Statistical Analyses

The primary analysis of the trial will be done in accordance with the "intent-to-treat" (ITT) principle, *i.e.*, all randomized participants will be included in the analysis. This means that once a participant is randomized to an intervention group, the participant's data will be included in the primary analysis regardless of compliance with the protocol-specified intervention or follow-up requirements.

A cox-proportional hazards model will be used to assess time to first occurrence of acute pancreatitis (primary outcome). Subjects without an outcome event will be censored at the last known status or at the end of study time point. We will adjust for duct diameter and number of attacks in the past 24 months in the primary analysis. Additional analyses will explore the impact of the other potential prognostic variables. This study is designed to test the primary hypothesis. However, it also offers the opportunity to conduct analyses to evaluate important additional patient outcomes. Details of the full analysis plan are in the Statistical Analysis Plan document.

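### Does the 33% minimum effect in Aim 1 and section 15.1 need a stated time point and scale, and a derivation for the 60% sham risk?

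*Combined protocol and SAP*

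**What the plan says.** Aim 1 in section 4.1 is headed "Reduce the risk of subsequent acute pancreatitis episodes by 33" per cent, with no time point, and continues "we will compare the incidence of acute pancreatitis > 30 days after treatment allocation as the primary outcome measure", treated as a time-to-event outcome.

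Section 15.1 says "we believe a minimum effect size of 33% (relative risk reduction) is of clinical relevance" and adds "This effect size was agreed upon by the site principal investigators as the least clinically significant benefit for ERCP". It next describes the outcome: "we propose a reduction in risk of subsequent acute pancreatitis during follow-up as the primary outcome, defined by the median time" to recurrence. The following sentence gives the design inputs: "We assume the risk of recurrence within 12 months of randomization is 60% in EUS + sham and 40% in EUS + ERCP" with miES, and medians of 9.1 and 16.3 months. The calculation assumes exponential hazards, two-sided alpha of 5%, 85% power and 20% non-adherence, and arrives at 234 patients (117 per group).

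Section 15.3 states: "A cox-proportional hazards model will be used to assess time to first occurrence of acute pancreatitis (primary outcome"). The analysis is by intention to treat.

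On follow-up, section 5.4 says "this would provide us with a minimum follow-up of 6 months and maximum follow-up of 48 months". Section 9.4.3 gives a minimum of 1 year.

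On the sham risk, section 15.1 cites 70% from a small trial with mostly 1-year follow-up. Section 3.3 describes that trial as 6/9 (67%) over a mean of 29 to 32 months.

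**The concern.** A relative risk reduction, a ratio of medians and a hazard ratio are different quantities, and a relative risk reduction depends on the time at which it is read. The text uses all three ideas without saying which one carries the 33%. Taken literally, a 33% reduction over follow-up is not what the trial is sized for.

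The stake would be interpretation. The site investigators agreed 33% as the smallest worthwhile benefit, and section 3.7.1 expects the result to expand or refute the practice. A reader who sees a Cox hazard ratio of 0.67 might say the 33% target was met, although at the design sham hazard that is only a 24% reduction in 12-month risk.

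The 60% sham risk also seems to lack a source. The one untreated recurrence figure given for divisum is described in two ways, and no step leads from it to 60%. If the true sham risk is lower, so is the power.

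**Working it through.** **Inputs.** From 15.1: 12-month risks of 60% and 40%, exponential hazards, two-sided alpha 5%, power 85%, non-adherence 20%. From 15.2: 1:1 allocation. From 5.4: follow-up of 6 to 48 months. Two assumptions are mine: uniform accrual, and non-adherence applied by dividing N by 0.8² (equivalently, multiplying the log hazard ratio by 0.8). The document does not say how the 20% enters.

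**Reproducing the plan's figures.**
- Sham hazard: −ln(0.4)/12 = 0.0764 per month. miES hazard: −ln(0.6)/12 = 0.0426.
- Medians: ln 2/0.0764 = 9.1 and ln 2/0.0426 = 16.3 months, as stated.
- Hazard ratio: 0.0426/0.0764 = 0.557. The ratio of the stated medians, 9.1/16.3 = 0.558, agrees.
- Events (Schoenfeld): 4 × (1.960 + 1.036)²/(ln 0.557)² ≈ 105.2, rounded up to 106.
- Mean event probability: 0.725 over 6 to 48 months, or 0.710 over 5 to 47 months (day-30 window removed).
- N: 106/0.725/0.64 = 228, or 106/0.710/0.64 = 233, against 234 stated. Power at 234 is 86% or 85%.

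**What 33% can mean under these inputs.** The relative reduction at time t is 1 − (1 − 0.6^(t/12))/(1 − 0.4^(t/12)).

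| Month | Reduction |
|---|---|
| 6 | 39% |
| 12 | 33% |
| 24 | 24% |
| 48 | 11% |

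Averaged over 6 to 48 months, the event probabilities are 0.811 and 0.639, a reduction of 21%. Only month 12 gives 33%, and month 12 is the time point that 15.1 attaches to its risks.

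**The other readings.**
- 33% as a hazard reduction (hazard ratio 0.667): miES 12-month risk 1 − 0.4^0.667 = 45.7%, reduction 24%, power 57 to 58% at 234.
- 33% as cumulative risk over follow-up: hazard ratio 0.41 to 0.42, power about 99%.

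Neither is compatible with 60% versus 40% at 12 months or with medians of 9.1 and 16.3.

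**Would judging the 33% on the observed 12-month risks help?** The analysis is by intention to treat and the design expects 20% non-adherence.
- If 20% of the miES arm behave as sham: 0.8 × 40% + 0.2 × 60% = 44%, a reduction of 1 − 44/60 = 27%.
- If the log hazard ratio is diluted by 0.8: exp(0.8 × ln 0.557) = 0.63, 12-month risk 1 − 0.4^0.63 = 44%, again 27%.
- In 4,000 simulated trials under each version (117 per arm, 6 to 48 months), the Kaplan-Meier 12-month reduction fell below 33% in about three quarters, although the full design effect held among adherers.
- Conversely, an observed hazard ratio of 0.667 corresponds to exp(ln 0.667/0.8) = 0.60 among adherers, a 29% reduction at 12 months.

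**Sham risk.** Power at 234 before any re-estimation, with the same allowance:

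| Sham 12-month risk | 33% at 12 months kept | Hazard ratio 0.557 kept |
|---|---|---|
| 45% | 68–69% | 78–79% |
| 50% | 74–75% | 81–82% |
| 60% | 85–86% | 85–86% |
| 70% | 94% | 89% |

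**Minimum follow-up.** Taking 12 to 48 months instead of 6 to 48 raises the mean event probability to 0.778 and power to 88%. The 6-month figure is therefore the cautious one of the two.

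**The case for a change.** The strongest case for a change is that a minimum effect agreed across sites should not have to be inferred, least of all when the sentence between the 33% and the 12-month inputs speaks of follow-up and medians. The primary analysis reports a hazard ratio, no target hazard ratio appears in the text, and the planned re-estimation cannot settle which scale was meant. With the 166 to 170 events expected at full adherence, a hazard ratio near exp(−2 × 1.96/√168) = 0.74 would be significant, yet it is only an 18% reduction at 12 months.

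Some of this stands. Section 4.1 would read better with a time point. The two accounts of the source trial and the two minimum follow-up times are real inconsistencies, and the step to 60% is not shown.

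The rest does not carry the point. Under exponential hazards, the 12-month risks, the medians and the hazard ratio are fixed by the same two hazards, so the scale follows by arithmetic. In any trial with 85% power, a significant estimate can fall short of the design effect, and naming the scale does not alter that. The documents use 33% for planning; nowhere do they make it a threshold for the observed estimate. On the sham risk, 15.1 calls 60% an assumption, says the natural history is poorly understood, warns that power may fall and plans a re-estimation. The 60% is also below the 70% it cites. If the 67% in section 3.3 is spread exponentially over 29 to 32 months, the 12-month risk is about 34 to 37%, but without event times that is only an illustration.

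**Conclusion.** The concern does not call for a change. The wording is loose, but the design inputs in the same paragraph fix the target as a 33% reduction in 12-month risk (60% versus 40%), equivalent to a hazard ratio of 0.56. The 234 patients and 85% power are right for that target, and the Cox model is a suitable test of it. An analyst following the plan would use the same sample size and test and reach the same conclusion whether or not the time point were written into 4.1. The 57 to 58% and 99% power figures belong to readings that the inputs rule out.

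The two descriptions of the source trial and the 6-month versus 1-year minimum follow-up are clerical slips. Neither alters the reproduced sample size. The sham risk is an acknowledged uncertainty, with power from about 68% to 94% across sham risks of 45% to 70% if a 33% reduction at 12 months is kept, and the plan already responds with a re-estimation. Using the observed 12-month estimate to decide whether 33% was reached would do harm, since about 27% is expected under the planned non-adherence.

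This rests on exponential hazards (the plan's own assumption), and on uniform accrual and the squared non-adherence inflation (mine, supported by how closely they return 234). The separate statistical analysis plan to which 15.1 and 15.3 refer is not in the reviewed text, so the re-estimation rule is not assessed here.

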15.2 Treatment Allocation

Enrolled patients will be assigned to either EUS + sham or EUS + ERCP with miES (1:1 randomization). A dynamic stratification system will be implemented to ensure well-balanced subgroups for the specified variables. Site, duct diameter (1, 2, 3, 4, 5, 6 or ≥ 7) and a dichotomized variable for number of attacks (1-2 vs ≥ 3) in the two years prior to randomization will be included in the randomization algorithm to ensure baseline balance between treatment arms. The superior balancing characteristics of dynamic randomization over blocked randomization have been well established. The randomization algorithm, which will be programmed into the data capture system, will employ biased-coin minimization and the variance method with stratification weights.

When a new patient is enrolled, the site will enter the stratification factor values into the eCRF (electronic case report form) on WebDCU™. The details of the randomization algorithm are located in the Randomization Plan study document.

15.3 Statistical Analyses

The primary analysis of the trial will be done in accordance with the "intent-to-treat" (ITT) principle, *i.e.*, all randomized participants will be included in the analysis. This means that once a participant is randomized to an intervention group, the participant's data will be included in the primary analysis regardless of compliance with the protocol-specified intervention or follow-up requirements.

A cox-proportional hazards model will be used to assess time to first occurrence of acute pancreatitis (primary outcome). Subjects without an outcome event will be censored at the last known status or at the end of study time point. We will adjust for duct diameter and number of attacks in the past 24 months in the primary analysis. Additional analyses will explore the impact of the other potential prognostic variables. This study is designed to test the primary hypothesis. However, it also offers the opportunity to conduct analyses to evaluate important additional patient outcomes. Details of the full analysis plan are in the Statistical Analysis Plan document.

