5.3 Study Sites

In order to achieve a targeted enrollment of approximately 234 randomized subjects during a 3.5-year period, we have identified sites who are regional referral centers for pancreatobiliary endoscopy. This would require approximately 67 patients/year at all sites, or 3-4 patients/year/site (assuming 16-20 enrolling sites). The choice of centers is deliberate to include those with high ERCP volumes and expertise in therapeutic endoscopy and pancreatitis care. The chosen centers include university-based and hospital-based practices; each site PI is a nationally or internationally recognized expert in ERCP, pancreatitis, or both.

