9.4.4 First acute pancreatitis during follow-up

Subjects will be instructed to contact the enrolling site if they develop signs or symptoms suspicious for acute pancreatitis. Blinded study personnel at the enrolling site will direct the follow-up if an enrolled subject develops signs or symptoms suspicious for acute pancreatitis (first episode) >30 days after enrollment. The decision to proceed with a clinical evaluation (e.g., laboratory testing, radiology, or referral to a medical facility for evaluation) will be made by a blinded site investigator who did not perform the index procedure and is unaware of the subject’s treatment allocation. Subjects will be given a standing order for laboratory testing and instructed to seek medical evaluation if symptoms reminiscent of their prior acute pancreatitis develop, and these symptoms are severe enough to interrupt their routine daily activities. If the subject received care for signs or symptoms suspicious for acute pancreatitis at another facility, medical

records will be requested for review. The blinded site investigator will determine if the subject's episode meets study criteria for acute pancreatitis.

Details of the acute pancreatitis event, such as need for and duration of hospitalization, presence of local and systemic complications of acute pancreatitis using the revised Atlanta criteria and treatment received will be assessed via history and review of medical records by the blinded coordinator and physician.

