12. OUTCOMES DEFINITIONS

12.1 Aim #1 Subsequent acute pancreatitis. The primary endpoint will be development of the first episode of acute pancreatitis during follow-up (following the 30-day post-randomization visit). The definition of acute pancreatitis will be the same as for study enrollment and per consensus (Atlanta guidelines):(Banks, Bollen et al. 2013) “The diagnosis of acute pancreatitis requires two of the following three features: (1) abdominal pain consistent with acute pancreatitis (acute onset of a persistent, severe, epigastric pain often radiating to the back); (2) serum lipase activity (or amylase activity) at least three times greater than the upper limit of normal; and (3) characteristic findings of acute pancreatitis on CECT and less commonly MRI or transabdominal ultrasonography.” If the patient is evaluated at the participating institution where randomization occurred, a blinded physician will assess for and determine if each of the three criteria are present. The blinded physician will diagnose acute pancreatitis if two of these three criteria are met. If the patient is evaluated and treated at another facility (not the primary site of enrollment), a blinded site coordinator will collect medical records pertinent to the encounter(s). These records will be reviewed by a blinded site physician at the participating institution where the

randomization procedure occurred. After reviewing these records, the blinded physician will diagnose acute pancreatitis if two of these three criteria are met.

12.2 Aim #2. Incidence rate ratio. The first secondary endpoint will be the incidence rate ratio of acute pancreatitis episodes. The incidence rate ratio will be defined by the (number of acute pancreatitis episodes/time post-randomization) divided by the (number of acute pancreatitis episodes/time pre-randomization), keeping person-time equal between the pre/post periods.

12.3 Exploratory Aim #3. Patient-reported outcomes. Pain related outcomes will include presence and pattern of pain, type of pain (neuropathic or nociceptive) using short form PROMIS instruments, opiate use (average use, recent use based on 30-day recall), and pain-related disability). Quality of life will be measured using the PROMIS Global Health and PROMIS 29 instruments. Patient's Global Impression of Change will be measured using the PGIC scale. Number and days of pain or pancreas-related hospitalizations will be quantified.

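### Site is balanced in the minimization but left out of the primary Cox model; adding it as a random effect would recover power if sites differ

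*Combined protocol and SAP*

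**What the plan says.** Section 15.2 lists the factors in the allocation algorithm: "Site, duct diameter (1, 2, 3, 4, 5, 6 or ≥ 7) and a dichotomized variable for number of attacks" in the two years before randomization. The method is biased-coin minimization with weights; the coin probability and weights are left to a Randomization Plan.

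Section 15.3 specifies a Cox model for time to first acute pancreatitis and states: "We will adjust for duct diameter and number of attacks in the past 24 months in the primary analysis". Everything else is deferred: "Additional analyses will explore the impact of the other potential prognostic variables". Site does not appear in 15.3 as a covariate, stratum, random effect or cluster. The section adds: "Details of the full analysis plan are in the Statistical Analysis Plan document". That separate plan is not part of the text reviewed here.

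Section 15.1 assumes that "the risk of recurrence within 12 months of randomization is 60% in EUS + sham and 40% in EUS + ERCP with miES groups". Section 5.3 foresees "3-4 patients/year/site (assuming 16-20 enrolling sites".

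**The concern.** Two of the three balancing factors enter the primary model and one does not, with no reason given. When allocation is balanced on a factor that predicts outcome, the treatment estimate varies less from trial to trial than under simple randomization. A model that omits the factor does not credit this, so its standard error is too large and the test is conservative. In a Cox model, omitting a prognostic factor also pulls the hazard ratio towards 1. Neither effect inflates type I error or biases the estimate under the null. What is lost is power.

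Sites could plausibly differ in recorded recurrence, in both arms alike, through ascertainment. Under section 9.4.4 the decision on work-up "will be made by a blinded site investigator who did not perform the index procedure". For episodes treated elsewhere, section 12.1 says "These records will be reviewed by a blinded site physician at the participating institution". No central adjudication of the endpoint is described.

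**Working it through.** **Inputs from the documents.** N = 234, two-sided alpha 5%, power 85%, non-adherence 20%, 12-month risks 60% and 40% (15.1); accrual 3.5 years, follow-up 6 to 48 months (5.4); 16 to 20 sites (5.3), so 234/20 = 11.7 to 234/16 = 14.6 patients per site.

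**Reproducing the plan's sample size.**
- Hazards: −ln(0.4)/12 = 0.0764 and −ln(0.6)/12 = 0.0426 per month. HR = 0.557, log HR = −0.584.
- Events (Schoenfeld): 4 × (1.960 + 1.036)² / 0.584² = 105.2, rounded up to 106.
- Event probability: 1 − (e^(−6λ) − e^(−48λ))/(42λ) = 0.811 (sham) and 0.639 (miES), mean 0.725.
- n = 106/0.725 = 146.2. Inflated for non-adherence, 146.2/0.8² = 228.4, within 3% of 234.

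**Assumptions not in the documents.** Between-site SD of the log hazard 0, 0.25, 0.5 or 0.75 (Gaussian); 18 sites; equal minimization weights and a 0.8 coin; duct diameter and attacks adjusted for but not prognostic. The SD is the variation left after those two covariates.

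**Effect simulated.** Non-adherence dilutes the log HR by 20%: 0.8 × (−0.584) = −0.467, HR 0.627 at SD 0. For SD > 0, the 60% and 40% are read as group risks, so the cumulative 12-month hazard H at the median site solves E[exp(−H·e^u)] = 0.40 for sham and 0.60 for miES, with u ~ N(0, SD²). At SD 0.5 this gives H = 0.912 and 0.483, ratio 0.530, diluted 0.530^0.8 = 0.601. The diluted site-conditional HRs at SD 0.25, 0.5 and 0.75 are 0.620, 0.601 and 0.572.

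To show what each SD means, the 12-month sham risk at sites 1 SD below and above the median site is 51% and 69% (SD 0.25), 43% and 78% (0.5), 35% and 86% (0.75).

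**Simulation.** 10,000 trials per setting, minimization on all three factors, follow-up uniform from 5 to 47 months after day 30, Wald tests; Monte Carlo SE about 0.35 points for power and 0.22 for null rejection.

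| SD | Power: planned model | + site random effect | stratified by site | Null rejection: planned | random effect | stratified | site fixed effects |
|---|---|---|---|---|---|---|---|
| 0 | 86.0% | 86.2% | 80.4% | 4.7% | 4.9% | 5.1% | 6.3% |
| 0.25 | 85.3% | 86.6% | 81.6% | 4.6% | 5.0% | 4.9% | 6.5% |
| 0.5 | 84.1% | 88.9% | 85.4% | 3.9% | 5.2% | 5.0% | 6.7% |
| 0.75 | 82.7% | 92.3% | 89.8% | 3.3% | 5.3% | 5.3% | 6.5% |

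The mean null HR is 1.00 throughout. The paired gain from the random effect is 0.2, 1.3, 4.8 and 9.6 points.

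**In patients.** Equivalent N ratio = ((1.96 + z of power with site)/(1.96 + z of power without))². At SD 0.5 this is ((1.96 + 1.221)/(1.96 + 0.999))² = 1.16. At SD 0.25 and 0.75 it is 1.04 and 1.36.

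**Other reading.** If the hazards in 15.1 are instead taken as those within a site, power without versus with the random effect is 84 vs 85%, 78 vs 84% and 68 vs 82% at SD 0.25, 0.5 and 0.75. Two separate simulations on this reading, 3,000 trials per setting, agree: 78 vs 84% and 79 vs 85% at SD 0.5, with null rejection of 4.2 vs 5.4% in both.

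**Sensitivity at SD 0.5, group-risk reading.** 16 sites: 83.7 vs 88.7%. 20 sites: 83.9 vs 88.7%. Very unequal site sizes: 83.5 vs 88.5%, null rejection 4.3 vs 5.9%.

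**The case against.** The strongest reply is that nothing is broken. The planned test controls type I error and, on the group-risk reading, keeps 83 to 86% power against a planned 85%. That stands, and it is why the point is optional.

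The gain depends wholly on an assumed SD. At 0.25 it is 1.3 points; gains near 5 points or more need site risks spread as widely as 43% to 78%. Several features may keep sites alike: similar referral centers (5.3), one two-of-three definition (12.1), standing laboratory orders (9.4.4) and six-monthly queries about hospital and emergency visits (9.4.3). Site differences that arise from case mix on duct diameter or attacks are already absorbed by the planned covariates. All this limits the size of the gain, not its direction.

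The random effect can also run above 5%: 5.9% in the sensitivity run with very unequal sites, although the separate simulations with unequal sites gave 4.9 to 5.6%. Taking 5.9% at face value and recalibrating to 5% by normal approximation lowers 88.5% power to about 87%, so about 1.5 of that 5.0-point gain would be excess test size. Most of the gain remains.

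Finally, the separate statistical analysis plan may already handle site. That cannot be settled from the text available, and the fix allows for it.

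**Conclusion.** The point holds as an efficiency improvement. Section 15.3 omits a factor that section 15.2 balances on. If sites differ, the planned test is mildly conservative (null rejection 4.6, 3.9 and 3.3% at SD 0.25, 0.5 and 0.75), and a site random effect gains about 1, 5 and 10 points of power, equivalent to about 4, 16 and 36% more patients. If sites do not differ, there is no measurable gain or loss. There is no type I inflation, no bias under the null, and no shortfall against the planned power on the group-risk reading.

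Confidence is medium: direction and cost are well supported, but the size rests on a residual between-site SD that the documents do not give and on an assumed coin and weights.

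**What to change.** In section 15.3, pre-specify site as a random effect (shared frailty) in the primary Cox model, alongside duct diameter and number of attacks, before any unblinded analysis. State the frailty distribution, estimation method, test, and what is done if the variance is estimated as zero or the model does not converge. If the statistical analysis plan already says how site is handled, make 15.3 agree with it.

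Stratifying by site is a workable alternative that holds its level (4.9 to 5.3%). With about 12 to 15 patients per site it costs about 6 points of power if sites do not differ (80 vs 86%) and 4 at SD 0.25 (82 vs 85%), but it beats the planned model at SD 0.5 (85 vs 84%) and 0.75 (90 vs 83%). Site fixed effects are not advised, given null rejection of 6.3 to 6.7%.

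The cost is a short addition to 15.3, and to the analysis plan if it is silent. The downsides are a slightly more complex model, a site-conditional HR as the reported estimate (mean 0.60 against 0.63 at SD 0.5), and possible null rejection a little above 5% with very unequal sites.
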